5.8 Withdrawal of Subjects

Although extremely unlikely, it is possible that a participant's participation in the study might be terminated by the investigator without regard to their consent. Instances in which termination could occur include excessive absences (>4) from psychotherapy sessions or extreme disruptiveness in sessions. The participant would be notified of termination in advance and in writing.

No adverse effects of termination from this study would be anticipated. However, the participant would not be likely to receive the benefits of full participation described above.

If you a participant is withdrawn from the study, no additional follow-up would be required. However, any data already collected prior to withdrawal from the study may be used by the investigators. No further information will be collected after a participant's withdrawal from the study.

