5.0 Study Procedures

5.1 Study Design

The project is a randomized superiority trial that compares change in mean pain severity and other outcomes in older Veterans (age 60-95 years) with chronic musculoskeletal pain who receive either Emotional Awareness and Expression Therapy (EAET) or Cognitive Behavior Therapy (CBT). The study includes 160 total participants, 80 randomly assigned to EAET and 80 to CBT. Each participant receives one 90-minute individual session and eight 90-minute group sessions based on the treatment condition (EAET or CBT) to which he/she is randomly assigned. Each EAET group at a time runs concurrently with one CBT group throughout the study. Group sessions consist of small groups of eight Veterans. All participants complete self-report questionnaires on pain, physical and psychiatric symptoms, and emotional well-being at baseline, post-treatment, and 6-month follow-up. Participants also complete self-report questionnaires on emotional approach coping, ambivalence over emotional expression, pain catastrophizing, and adaptive pain coping skills at baseline, post-treatment, and 6-month follow-up. Participants complete a working alliance questionnaire at post-treatment. The data are used to assess the superiority of EAET compared to CBT on change in mean pain severity scores from baseline to post-treatment (primary outcome) and 6-month follow-up and change in other patient-centered outcomes (PCO) from baseline to post-treatment and 6 month-follow-up (secondary outcomes). In addition, the data are used to test mediation of EAET by improved emotion regulation (greater emotional approach coping and decreased ambivalence over

emotional expression), mediation of CBT by improved cognitive and behavioral coping (decreased catastrophizing and increased pain coping skills), and mediation of both treatments by strength of the working alliance. Finally, the data are used to test whether higher baseline depression and anxiety predict response to EAET and lower baseline depression and anxiety predict response to CBT.

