Finally, we post flyers on VA bulletin boards and at identified locations in the aforementioned clinics, and prospective Veterans are self-referred to research staff through these flyers. A waiver for consent and documentation of consent for recruitment/screening only is being sought from the IRB. Patients who are unable to give informed consent or have a legal conservator are not included in the study. Only in cases in which a patient's capacity to provide informed consent is questionable (according to the clinician's best judgement) will they be required to complete the UCLA Capacity for Consent Form to determine whether they may be included in the study. Patients who have assigned payees are compensated accordingly.

Payments:

After completing the baseline visit (baseline questionnaires), participants will receive \$50. After completing posttreatment questionnaires (Week 9), participants will receive \$50. After completing 6-month follow-up questionnaires (Week 39), participants will receive \$50. Participants receive a check, which is mailed within three weeks of completing the aforementioned study procedures.

Proposed payments are provided for participant time, inconvenience, and transportation to complete research procedures (i.e., questionnaires). Substantial time is needed in order to complete the battery of questionnaires. In addition, driving in Los Angeles can be challenging, with many participants driving a considerable distance. Thus, payments are modest. Participants are not reimbursed for attendance at psychotherapy sessions.

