5.3 Informed Consent Procedures

After a Veteran has expressed interest in the study, the PI or other research team member discusses the details of the study, including study procedures, risks, and benefits, with the Veteran by phone or in person. There is an opportunity to ask questions, to have information clarified, and for potential participants to discuss the study with other family members. Standardized demographics and medical history are obtained, as well as psychiatric diagnoses and substance use disorder status. All patients complete the MMSE for screening purposes. If the potential participant meets screening criteria, he/she is invited to enroll as a primary research participant. Those who fail to meet the inclusion/exclusion requirements are thanked for their time. Interested participants come to meet in person with the PI or another research team member to enroll in the study. Consent and HIPAA forms are reviewed with the participant prior to the start of the study. As the need arises, decision-making capacity is assessed by a member of the research team who is a psychiatrist or licensed psychologist. The UCLA Capacity to Consent Form will be used for this purpose. Baseline assessments are then completed. Finally, the Veteran is randomized and scheduled for an individual preparatory session based on treatment assignment (described below).

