5.5 Study Evaluations

Data are collected from participant self-report before, after, and at 6-month follow-up from interventions. Descriptive measures collected at baseline include demographics (age, sex, race/ethnicity, marital status, education) and clinical characteristics (medical comorbidities, medications, psychiatric diagnoses, substance use). Mini-Mental State Examination is collected at screening.

Primary Outcome: The primary outcome is change in mean pain severity scores on the Brief Pain Inventory (BPI) (70) from baseline to post-treatment. The BPI is a short, self-administered questionnaire that was developed for use in cancer patients but is now one of the most widely used tools for assessing a variety of pain conditions in clinical and research settings (71, 72). The BPI contains four items rated 0-10 assessing worst and least pain during the last seven days, as well as average pain and current pain. The mean of these four items is determined to assess mean pain severity. This metric is referred to alternately in the literature as “mean pain severity” and the “pain severity index” (24).

Secondary Outcomes: Consistent with recommendations from IMMPACT (73) and our pilot data, we examine pain interference, physical symptoms (sleep disturbance, fatigue), emotional symptoms (anxiety, depression, PTSD symptoms), purpose and meaning, patient-reported global impression of change, and satisfaction with treatment as secondary outcomes. PROMIS and NIH Toolbox measures are used, where available, because of their long-term potential to improve standardization of patient-reported outcomes (79).

Potential Moderators: Based on previous literature and our pilot work, we examine whether greater baseline anxiety or depression predict greater response to EAET on primary and secondary outcomes post-treatment and at follow-up, and lower baseline anxiety or depression predict greater response to CBT on primary and secondary outcomes post-treatment and at follow-up. We use the same PROMIS measure to evaluate baseline anxiety and depression as used for secondary outcomes.

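### Section 5.8 ends data collection together with therapy, so a participant terminated by the investigator during the sessions has no post-baseline pain score for the intent-to-treat analysis (minor, cheap to improve)

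*Combined protocol and SAP*

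**What the plan says.** Section 5.8 recognises one status, termination or withdrawal from the study as a whole. It opens "Although extremely unlikely, it is possible that" the investigator may end participation without the participant's agreement. The grounds are an open list: "Instances in which termination could occur include excessive absences (>4) from psychotherapy sessions or extreme disruptiveness in sessions". After withdrawal, "no additional follow-up would be required", earlier data may still be used, and "No further information will be collected after" that point. The section describes neither an exit assessment nor a status in which sessions stop and questionnaires continue.

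Elsewhere the protocol expects complete assessment. Section 5.1 says: "All participants complete self-report questionnaires on pain, physical and psychiatric symptoms, and emotional well-being at baseline, post-treatment, and 6-month follow-up". Section 5.5 says: "Data are collected from participant self-report before, after, and at 6-month follow-up from interventions", and its Table 2 schedules BPI severity at those three times only. The Payments text in Section 5.2 places the first post-baseline questionnaire at Week 9 ("After completing posttreatment questionnaires (Week 9), participants will receive" $50) and the last at Week 39.

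Section 5.7 analyses change from baseline in a mixed model under intent to treat, relies on data being missing at random, and plans for up to 25% dropout.

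**The concern.** Both named grounds for termination concern conduct in therapy, yet the consequence extends to outcome measurement. By Section 5.3, "the Veteran is randomized and scheduled for an individual preparatory session", so absences and disruptive behaviour arise after allocation and could differ between the two therapies. Outcomes that some of these participants might willingly give would not be requested.

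The primary model takes change from baseline as its outcome and does not model post-treatment pain with baseline pain as a predictor. A participant with only a baseline score supplies no outcome row. For that person, the missing-at-random assumption amounts to supposing that the unseen change resembles that of others in the same arm, apart from any covariates added.

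The Dropouts text in Section 5.7 does not supply what is missing. Its dropout regression uses baseline covariates, and its completer subanalyses leave out the same people.

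This does not contradict Section 5.7, which openly allows for missing data. It is an avoidable part of the loss, and one tied to post-randomization behaviour.

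**Working it through.** **Reproducing the plan's figure.** Section 5.7 needs 60 evaluable per arm and allows 25% loss: 60 / (1 − 0.25) = 80 per arm. This matches the plan and leaves 0.25 × 80 = 20 losses per arm.

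**Scores available after termination during the sessions.** The schedule has two post-baseline BPI assessments, Week 9 and 6 months. Someone terminated before Week 9 has neither. Someone terminated after Week 9 already has the primary score, which Section 5.8 allows to be used. The concern is therefore limited to terminations during the sessions.

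**Inputs from Section 5.7.** Pilot mean improvements are 1.13 (EAET) and 0.33 (CBT), a difference of 0.80. The detectable difference is 0.70 points at 80% power.

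**Assumptions, because the documents give no figures.**
- The number terminated is 1 to 2 of 80 per arm, chosen to fit the protocol's view that this is very rare.
- Retained participants show the pilot means.
- f is the mean change in terminated participants as a fraction of the retained mean in their arm: 1 is the same change, 0 is none, −1 is worsening of equal size.

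**Formula.** With pE and pC the proportions terminated in EAET and CBT:

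all-randomized difference = 1.13 × [1 − pE(1 − f)] − 0.33 × [1 − pC(1 − f)]

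shift = 0.80 − that difference

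| Terminated (EAET, CBT) | f | All-randomized difference | Shift |
|---|---|---|---|
| 1, 1 | 0 | 0.790 | 0.010 |
| 2, 2 | 0 | 0.780 | 0.020 |
| 2, 1 | 0 | 0.776 | 0.024 |
| 0, 1 | 0 | 0.804 | −0.004 |
| 1, 1 | 0.5 | 0.795 | 0.005 |
| 2, 2 | 0.5 | 0.790 | 0.010 |
| any | 1 | 0.800 | 0 |
| 1, 1 | −1 | 0.780 | 0.020 |
| 2, 2 | −1 | 0.760 | 0.040 |

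For example, for 2 EAET and 1 CBT at f = 0: 1.13 × 78/80 − 0.33 × 79/80 = 1.1018 − 0.3259 = 0.776.

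Against the detectable difference, 0.010 / 0.70 = 1.4% and 0.020 / 0.70 = 2.9%.

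**Other pilot means.** Section 2.0 gives pilot reductions of 1.44 and 0.39, a difference of 1.05. At f = 0 the shift is 1.05/80 = 0.013 for 1 per arm and 2 × 1.05/80 = 0.026 for 2 per arm.

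**What continued collection would recover.** If a share q of those terminated answer, the estimated arm mean is m(1 − p + qpf) / (1 − p + qp), where m is the retained mean. At f = 0 and q = 0.5:
- 1 per arm: 0.80 × 79/79.5 = 0.7950, so 0.005 is recovered.
- 2 per arm: 0.80 × 78/79 = 0.7899, so 0.010 is recovered.

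At q = 1 the full 0.010 or 0.020 is recovered.

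**Power.** The plan does not print the SD. Solving back from 0.70 points, 60 per arm, 80% power and two-sided 0.05 gives about 1.37. Terminations that fall within the 20 allowed losses leave power at 80%. If 2 per arm (2.5%) came on top of them, 58 would remain per arm and power would be 78.7%.

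**The case against.** The strongest objection is that the effect is negligible. With the implied SD of 1.37, the standard error of the difference at 60 per arm is 1.37 × √(2/60) = 0.25. Recovering 0.005 to 0.010 points is then 2% to 4% of one standard error, and the termination rate behind it is assumed. This stands, and it is why the point is minor.

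The exposed group is also narrow. Termination is discretionary, and missing more than four sessions does not by itself end data collection. Participants who are not terminated remain under the Section 5.1 schedule. This also stands.

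The protocol is not wholly silent. Section 6.0 provides for suspending psychotherapy on safety grounds without calling it withdrawal, and the Dropouts text in Section 5.7 says sensitivity analyses will be considered to gauge bias. However, Section 6.0 does not mention later questionnaires. The sensitivity analyses are optional, follow only if dropout is judged not completely at random, and cannot supply scores that were never requested.

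Analysis in the assigned arm is already implied by intent to treat, so the new elements are the request for questionnaires and the count by arm. The consent pages were not available for review, so the consent wording needed, and any re-consent of enrolled participants, cannot be costed.

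**Conclusion.** The concern holds as a minor design point. As written, Section 5.8 stops outcome collection for anyone the investigator terminates, and a termination during the sessions leaves no change score for the primary analysis.

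Assuming 1 to 2 terminations per arm and no change in those participants, the shift in the treatment difference is 0.010 to 0.020 points. Across the cases worked above it runs from −0.004 to 0.040, and it is zero if terminated participants change as much as the others. The direction cannot be known in advance. The sample size stands while terminations fall within the 25% allowance.

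The reading of the text and schedule is firm, but the rate and the outcomes of terminated participants are assumptions. The reason to act is the low cost, not a large bias.

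**What to change.** In Section 5.8, separate the end of sessions from the end of data collection. State that a participant whose sessions the investigator ends, for absences, disruptiveness or any other reason, is still asked for the post-treatment and 6-month questionnaires unless they withdraw consent for data collection, and is analysed in the assigned arm. Report the number of investigator terminations by arm. Whether and when sessions are ended stays as the protocol has it.

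The cost is protocol and consent wording, staff time to contact these participants, and the existing $50 per completed questionnaire visit. That is up to 2 × $50 = $100 per person, or at most $200 to $400 for 2 to 4 participants across both arms. Some will not respond, so the loss is reduced and not removed.

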6.0 Reporting/Risks/Safety

Reporting:

In the event of an unanticipated problem, serious adverse event, or protocol deviation, this information will be reported immediately to the IRB according to IRB policy by submitting a Form 5.

In addition, data and safety monitoring for this study will be provided by the Clinical Science Research & Development (CSR&D) centralized Data Monitoring Committee (DMC). The DMC is provided by CSR&D to ensure independent oversight of the safety and integrity of the project. The DMC is an independent multidisciplinary group, whose members have collectively – through research, education, training, experience, and expertise – the requisite knowledge pertinent to the subject areas to be reviewed.

Membership details are available on the CSDR website. The DMC will provide an ongoing independent evaluation of this study focused on safety and feasibility, including participant accrual and retention, adverse events monitoring, and data analyses.

Meetings will be held three times per year at which recommendations will be made to the Director of CSR&D for endorsement. These recommendations will range from approval to continue (unconditionally or with conditions to be addressed) to probation or possibly termination, if there are problems with enrollment or safety concerns.

Risks and Risk Minimization:

Clinical interview, psychotherapy interventions, and questionnaires: no major risks. Minor risks include inconvenience, frustration with questions, sadness or distress with discussing emotional experiences, and potential embarrassment if the confidentiality of research records is breached. We minimize breach of confidentiality by keeping all participant data in a locked cabinet. Regarding psychotherapy specifically, participants may feel discomfort disclosing personal information to the therapist and other group members. Participants are also at risk for nonresponse or limited response to treatment but are always free to end participation in the study and pursue alternate treatment if they so choose.

We will be monitoring for safety of participants throughout the study. At the beginning of each therapy session, there will be a verbal check-in period in which patients can discuss any worsening of symptoms, or any suicidal ideation. In addition, in case of worsening of symptoms between sessions, the participant will be provided with the PI's direct [contact]), in addition to the telephone number for his/her therapist and other study personnel, and the participant will be encouraged to call.

On check-in or upon receiving a phone call from the participant, if the participant is found to have worsening of physical medical symptoms (e.g., pain), the patient's primary care provider will be contacted, and a close follow-up appointment will be obtained for the participant. In the event of worsening psychiatric symptoms (e.g., depression, anxiety), the patient may be referred to their mental health provider, or a referral may be placed to the Geriatric Psychiatry Outpatient Program in the even the participant does not have a primary mental health provider. In the event of suicidal or violent ideation, the participant will be referred immediately to the emergency department or to 911, as outlined in our suicide safety plan below.

In the event of worsening physical or medical symptoms, study procedures (i.e., psychotherapy) will be suspended after a conversation with the participant, if that is the

participant's preference. In the event of suicidal or violent ideation, study procedures (i.e., psychotherapy) will be suspended immediately.

Suicide Safety Plan:

We do not expect any study participants to develop suicidal ideation in this treatment study for chronic pain. However, it is known that chronic pain patients have twice the rate of suicide of those without chronic pain. Therefore, we have a suicide safety plan in place. Research physicians and the research psychologist are clinicians in geriatric psychiatry, and each session will begin with a verbal check-in period, and assessments will be completed periodically to monitor for depression. If researchers feel that the participant is at risk for suicide and/or a threat to others while he/she is present at WLA either undergoing clinical interview, completion of assessments, therapy sessions, or other study procedures, he/she will be evaluated by a trained research physician or psychologist who is a study team member and brought to the WLA ER if psychiatric hospitalization is thought to be required. All Veterans will have the PI's direct [contact]) to call in the event of worsening symptoms and will also be instructed to dial 911 or report to the nearest ER if a psychiatric emergency, such as suicidal or violent ideation, occurs during the study but while the Veteran is not present at WLA. If a Veteran participant is noted to have significant depression but is not suicidal, the research team will discuss the benefits of treatment and provide contact information for the GLA Geriatric Psychiatry Outpatient Program.

Potential Benefits:

The study will be of direct relevance and benefit to older Veterans who suffer from chronic pain. All study participants will receive a psychological intervention, either standard treatment (CBT) or a promising experimental treatment (EAET). We anticipate this could be of benefit for participants on pain and related outcomes, such as mood, anxiety, sleep, and fatigue. Results from the study will inform future research on psychological interventions for chronic pain and contribute to understanding the psychological change processes involved in improvements in chronic pain.

Risk/Benefit Ratio:

The risks of this study are small. We will be gaining valuable information to help improve our understanding of the psychological processes involved in improvement in chronic pain and help inform research aimed at using alternate psychological treatment strategies for older adults with chronic pain.

Alternatives to Participation:

The patient may receive ongoing medical care in their respective clinics, including in primary care, pain clinic, Women's Clinic, etc. for pain whether or not s/he participates in the study. This includes medications and interventional pain approaches (e.g. injections, ketamine). The VA also offers a chronic pain rehabilitation program, cognitive behavior therapy for chronic pain, and physical and occupational therapy for chronic pain. Mindfulness classes, acupuncture, and other complementary/integrated medicine approaches are also offered. The patient may elect to not participate, and this will not adversely affect any ongoing care at the VA.

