5.2 Recruitment Methods

Participants:

The study includes 160 Veterans age 60-95 years (2 treatment conditions x 10 groups x 8 Veterans = 160) with chronic musculoskeletal pain. Veterans are recruited from outpatient clinical sites at West Los Angeles Veterans Affairs Medical Center (WLA), the largest VA Medical Center on the West Coast. We have already partnered with several clinical sites, including Geriatric Psychiatry, Geriatrics, Chronic Pain, Interventional Pain, Women's, and Primary Care Clinics, for our pilot, and plan to use these sites for this project as well. In our pilot, we were able to recruit 48 participants from our clinical sites in 30 weeks. For the proposed trial we have a similar recruitment schedule of approximately 1-2 Veterans per week, in order to complete all treatments and 6-month follow-ups by the end of Year 4, leaving Year 5 for data clean-up and analysis. The schedule in Table 1 indicates recruitment goals for the duration of the study.

Table 1: Enrollment for Each Year	Year 1	Year 2	Year 3	Year 4	Year 5
Screening, Baseline Assessments, EAET, Post-Treatment and 6-month Follow-Up Assessments	24	24	16	16	-
Screening, Baseline Assessments, CBT, Post-Treatment and 6-month Follow-Up Assessments	24	24	16	16	-

Recruitment and Screening Procedures:

Approved clinician and patient flyers are distributed to clinic staff in participating programs (see attached). Before clinic, a medical chart review is performed to determine whether potential Veteran participants meet basic inclusion/exclusion criteria. Clinicians not associated with the study will passively recruit patients by handing them a flyer and referring them to the research team. No Veteran is approached by research staff without having previously agreed to such contact with his/her clinician.

In addition, we will screen additional medical charts using a VA Data Warehouse generated list of veterans aged 60 and older, who carry a diagnosis of low back pain, and are actively receiving care from a VA PCP. Patients identified as eligible this way will be mailed a letter and a flyer about the study. Only patients who reach out to the research team will be considered for enrollment in the study and will not be contacted otherwise.

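### Safety monitoring is promised for the whole study, but nothing is scheduled between post-treatment and the 6-month visit, and neither visit has a structured adverse-event enquiry

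*Combined protocol and SAP*

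**What the plan says.** Section 6.0 (Reporting/Risks/Safety) opens its monitoring text with "We will be monitoring for safety of participants throughout the study". Two mechanisms follow. The first is tied to treatment: "At the beginning of each therapy session, there will be a verbal check-in period in which patients can discuss any worsening of symptoms". Suicidal ideation is covered at the same check-in. The second covers the time between sessions: telephone numbers are supplied and "the participant will be encouraged to call". The responses to worsening that are set out next start from one of these two events.

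The Suicide Safety Plan in the same section repeats the check-in and adds that "assessments will be completed periodically to monitor for depression". It also provides for evaluation of a participant thought to be at risk while on site, "either undergoing clinical interview, completion of assessments, therapy sessions, or other study procedures".

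Table 2 (section 5.5) places the PROMIS depression form at baseline, post-treatment and 6-month follow-up. Section 5.2 (Payments) puts the post-treatment questionnaires at Week 9. For the last assessment it reads "After completing 6-month follow-up questionnaires (Week 39". Section 6.0 (Reporting) gives adverse-event monitoring to a central DMC that meets three times a year.

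**The concern.** A reader of section 6.0 would expect some active safety enquiry over the whole of participation. The visit schedule does not supply it once therapy ends, and the two assessments after therapy are described as questionnaire visits with no adverse-event question attached.

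What is at stake is the ascertainment of harms. The protocol itself notes that people with chronic pain have twice the suicide rate of those without, and it asks the DMC to watch adverse events. A DMC can review only what is collected. If late events are recorded mainly when a participant chooses to report them, a low count after Week 9 is hard to interpret: events may have been rare, or they may not have been asked about. The trial reports efficacy at 6 months, so its account of events over the same period should rest on a comparable enquiry in both arms.

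**Working it through.** **Inputs**
- Sessions: one individual plus eight weekly group sessions (section 5.6), so 1 + 8 = 9 sessions.
- Post-treatment at Week 9 and 6-month follow-up at Week 39 (section 5.2, Payments).
- Enrolment 160; planning dropout up to 25% (section 5.7).
- Assumption: both week labels count from the same start. The protocol does not define Week 0.

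**Step 1: the printed follow-up week.** Week 9 agrees with nine weekly sessions. Week 39 does not agree with six months counted from Week 9:
- 9 + 26 = Week 35.
- Counting backwards, 39 − 26 = 13, so Week 39 is six months after Week 13, not after Week 9.

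The two labels conflict, so the gap is given both ways.

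**Step 2: length of the interval with no scheduled contact.**
- Printed labels: 39 − 9 = 30 weeks; 30/39 = 77%.
- Six months from Week 9: 35 − 9 = 26 weeks; 26/35 = 74%.

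**Step 3: exposure in that interval.**
- Upper end, no dropout and 30 weeks: 160 × 30/52 = 92 person-years.
- Lower end, 25% dropout and 26 weeks: 160 × 0.75 = 120, and 120 × 26/52 = 60 person-years.

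**Step 4: what is scheduled in each period.**

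| Period | Verbal check-in | Depression form | Structured adverse-event enquiry | Other route |
|---|---|---|---|---|
| Baseline | not stated | yes | not stated | on-site at-risk evaluation |
| Therapy, to about Week 9 | every session | none | not stated beyond the check-in | participant's call; on-site at-risk evaluation |
| Post-treatment visit | not stated | yes | not stated | on-site at-risk evaluation |
| Between the two visits (26 to 30 weeks) | none | none | none | participant's call |
| 6-month visit | not stated | yes | not stated | on-site at-risk evaluation |

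Set against Table 2, the periodic depression assessments of section 6.0 are two after baseline: one at post-treatment and one at 6 months. No section says who reviews them for safety, or when.

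**The case against.** The strongest reply is that safety is covered more fully than the session check-in alone suggests, and much of that reply stands.

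- A reader might infer that therapy sessions hold the only active check. The documents do not support this. Section 6.0 gives depression monitoring as a purpose of the assessments, Table 2 places them at both later visits, and the at-risk evaluation expressly includes assessment visits. The gap lies between two assessments.
- A reader might infer that the absence of a depression scale during therapy creates the gap. It does not. Every session has a check-in on worsening and suicidal ideation, and the gap arises only from the lack of contact after post-treatment.
- A reader might take section 5.2, "leaving Year 5 for data clean-up and analysis", to mean that questionnaires go unread until then. That phrase concerns the trial's data clean-up and analysis. Earlier review for safety is unstated, not excluded.
- A reader might infer that no safety statement at 6 months would be possible. Pain, depression, anxiety, PTSD symptoms and global change are all asked at 6 months in both arms. Section 5.4 also records medications and other treatments at the later visits, so worsening on those measures can be reported.

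Other mitigating facts are the IRB reporting, the DMC, the exclusion of active suicide or violence risk in the past 6 months, and the continuing VA care that participants may receive. The DMC and IRB work at study level, however, and depend on what is collected from participants. None of these supplies a scheduled question about events at the post-treatment or 6-month visit, so that narrower omission remains.

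**Conclusion.** The point holds in a limited form. The promise of study-long monitoring does not match the schedule: for about three quarters of participation (74% to 77%, 26 to 30 weeks) no contact is scheduled and the only described route is the participant's own call. At the visits on either side of that interval, symptoms are measured, but no structured adverse-event enquiry and no timing of safety review is stated. Late events such as hospital or emergency visits would therefore reach the DMC mainly if volunteered.

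The exposure concerned is about 60 to 92 person-years. The top figure assumes no dropout. The lower one applies the full 25% dropout and the shorter interval. Both rest on the assumption about the week labels. The primary outcome and its analysis are not affected; the consequence is for the completeness of harms data and for what the final report can say about late events.

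**What to change.** - In section 6.0 and Table 2, add the existing session check-in questions and a standard adverse-event question (including hospital and emergency visits since last contact) at the post-treatment and 6-month visits. Ask them in the same way in both arms, and log the answers as adverse-event data for the DMC.
- Reconcile the two statements in section 6.0, on monitoring over the whole study and on periodic depression assessment, with Table 2. State which periods are monitored and by what means, and when the questionnaires are reviewed for safety.
- Reconcile Week 39 with the 6-month label and define Week 0.

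Any score threshold, escalation rule or extra contact between the two visits is for the sponsor's clinicians to decide and is not proposed here.

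The cost is a few minutes at two visits that already exist, plus wording changes. More events will be recorded and will need processing.
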